An episode is defined as the interruption and then re-initiation of IP, regardless of the duration of the interruption. The fourth interruption should be considered permanent when based on the above criteria.

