6.12. Retest Requirements for Subjects With Changes in Kidney Function

Retesting of laboratory values, including sCr and eCrCl, as well as the interruption of IP due to safety concerns, can occur any time on study at the Investigator's discretion.

If a subject experiences any of the following changes in kidney function (using central laboratory results), the subject must return to the site for retesting and be evaluated for potential contributing factors:

- eCrCl declines >30% from Baseline in the period starting at Baseline through Month 12 study visit, or eCrCl declines >40% from Baseline in the period from the Month 12 study visit through the Month 24 study visit.
- Absolute sCr \geq 4.0 mg/dL or eCrCl <20 mL/min at any time on study (Note: this is also the criteria for when IP must be interrupted; see Section 6.12.1.)

The underlying cause of the change in kidney function should be evaluated, treated, and managed as medically appropriate by the Investigator. Additional information will be collected on these events in the CRFs.

During any Retest periods throughout the study period, IP does not need to be interrupted unless warranted as determined by the Investigator and treating Healthcare Providers or if specific criteria are met (sCr \geq 4.0 mg/dL or an eCrCl < 20 mL/min; see Section 6.12.2).

For IP discontinuation criteria see Section 5.3.2.1.2. Retesting schema for subjects with changes in kidney function is presented in Appendix C.

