6.12.2. Absolute Serum Creatinine ≥ 4.0 mg/dL or Estimated Creatinine Clearance <20 mL/min

If a subject experiences an absolute sCr ≥ 4.0 mg/dL or an eCrCl <20 mL/min at any time during the study, IP must be **temporarily interrupted**, and the subject will return to the site within 1 to 2 weeks (Retest 1) for a retest.

Baseline Through the Month 12 Study Visit

- From Baseline through the Month 12 study visit, if any retest eCrCl declines $\leq 15\%$ from Baseline and sCr <4.0 mg/dL and an eCrCl ≥ 20 mL/min, no further retests are required and the subject may restart IP, at the Investigator's discretion, and continue the protocol-scheduled visits. The re-initiation of IP may occur regardless of the duration of the interruption.

- If Retest 1 eCrCl declines >15% from Baseline or sCr \geq 4.0 mg/dL or an eCrCl <20 mL/min, the subject will return to the site for a retest approximately 3 to 4 weeks (Retest 2) after the initial decline was noted.
- If Retest 2 eCrCl declines >15% from Baseline or sCr \geq 4.0 mg/dL or an eCrCl <20 mL/min, the subject will return to the site for a retest approximately 7 to 8 weeks (Retest 3) after the initial decline was noted.
- After Retest 3, subjects should continue the protocol-scheduled visits. If eCrCl is \leq 15% of the Baseline and sCr <4.0 mg/dL and eCrCl \geq 20 mL/min, the subject may restart IP, at the Investigator's discretion.

Month 12 Study Visit to Month 24 Study Visit

- From the Month 12 study visit to the Month 24 study visit, Retests 2 (Weeks 3 to 4) and 3 (Weeks 7 to 8) should be performed if eCrCl declines >20% from Baseline or sCr \geq 4.0 mg/dL or eCrCl <20 mL/min.
- If any retest eCrCl declines \leq 20% from Baseline and sCr <4.0 mg/dL and an eCrCl \geq 20 mL/min, no further retests are required and the subject may restart IP, at the Investigator's discretion, and continue the protocol-scheduled visits. The re-initiation of IP may occur regardless of the duration of the interruption.

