8.3.3. Month 24 (± 7 Days) and/or End of Treatment Visit

The following procedures and assessments will be performed at Month 24 (for subjects who complete the Treatment Period) or as soon as possible after permanently discontinuing IP (for subjects who discontinue IP early):

- Collect reasons for discontinuing IP, if applicable.
- Administer patient-reported outcome assessments.
- Review gout flares that occurred since the last study visit.
- Take vital signs.
- Measure weight.
- Assess AEs.
- Record concomitant medications.
- Assess compliance with IP (lesinurad/placebo).
- Assess compliance with XO1.

- Measure target tophi.
- Collect blood sample for hematology.
- Collect blood sample for the following serum chemistry analyses:
 - Analytes 1.
 - Analytes 2.
 - Analytes 3.
 - Pregnancy test for females of childbearing potential.
- Collect blood sample for plasma biomarkers.
- Collect urine sample for the following analyses:
 - Urinalysis.
 - Protein-creatinine ratio.
 - Urine biomarkers.
- Dispense XOI.

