8.4. Follow-Up Period

All subjects who complete the Treatment Period will return to the site for an End of Study Visit 1 month later ([Section 8.4.2](#)).

Subjects who permanently discontinue IP early should return to the site for an End of Treatment visit ([Section 8.3.3](#)) as soon as possible after discontinuing IP, then a Post-End of Treatment Visit ([Section 8.4.1](#)) 1 month after the End of Treatment Visit. They should remain on study and follow the protocol schedule (with the exception of dispensing and taking IP) and have an End of Study Visit ([Section 8.4.2](#)) at the conclusion of their study period. Alternatively, if the subject does not agree to this option, a modified follow-up including, eg, regular telephone contacts or a contact at Month 24, should be arranged, if agreed to by the subject and in compliance with local data privacy laws/practices. Subjects who do not wish to continue on study after discontinuing IP should complete an End of Study Visit 1 month after treatment discontinuation ([Section 8.4.1](#)), which should be performed in place of the Post-End of Treatment Visit.

8.4.1. Post-End of Treatment Visit for Subjects Who Discontinue Investigational Product But Remain on Study (~30 Days Post-Discontinuation)

Subjects who permanently discontinue IP but remain on study should complete a Post-End of Treatment Visit approximately 28 days after the End of Treatment Visit. The following procedures and assessments will be performed:

- Administer patient-reported outcome assessments.
- Review gout flares that occurred since the last study visit.
- Take vital signs.
- Assess AEs.

- Record concomitant medications.
- Measure target tophi.
- Collect blood sample for hematology.
- Collect blood sample for the following serum chemistry analyses:
 - Analytes 1.
 - Analytes 2.
 - Analytes 3.
- Collect urine sample for the following analyses:
 - Urinalysis.
 - Protein-creatinine ratio.
- Assess compliance with XOI, if applicable.
- Dispense XOI, if applicable.

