9. PLANNED STATISTICAL METHODS

This section describes the statistical considerations and data analyses to address the objectives of the study. Further details will be provided in the Statistical Analysis Plan (SAP).

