9.4.2.1. Change From Baseline in Estimated Creatinine Clearance

Absolute and percent changes from Baseline to Month 24 in eCrCl will be assessed using a MMRM analysis that includes terms for treatment (LESU + XOI and PBO + XOI), visit, treatment by visit interaction, stratification factors (type of XOI [allopurinol or febuxostat], Baseline measurable target tophi status [present/absent], and Screening eCrCl [30.0 to <45.0 mL/min or 45.0 to <60.0 mL/min], as appropriate as stated in [Section 9.1](#)), and Baseline eCrCl as covariate. The model will assume an unstructured covariance matrix. If convergence issues are encountered, alternative covariance structure will be explored (details will be provided in the SAP). Least-square (LS) mean by treatment and LS mean difference between LESU + XOI and PBO + XOI alone will be estimated from the MMRM analysis, along with the 95% CI of LS mean difference.

All subjects should be followed for safety events even if they discontinue IP (lesinurad or placebo), as permitted. Prior to performing MMRM analysis, renal function data that are collected after subjects discontinue IP will be set to missing. All missing data will be imputed using multiple imputation methodology assuming MAR and separate imputation models for the LESU + XOI and PBO + XOI groups. Sensitivity analysis will include all available data (including data after subjects discontinue IP) and impute only for missing data assuming MAR. Additional sensitivity analysis will be performed using multiple imputation assuming missing not at random, depending on the nature of missing data and early treatment discontinuations (eg, subjects discontinuing early due to worsening renal function).

In addition to using the Cockcroft-Gault equation for eCrCl, renal function will also be evaluated using estimated glomerular filtration rate (eGFR) equations (eg, the Modification of Diet in Renal Disease [MDRD]), and may be explored using similar methods as above.

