APPENDIX A. SCHEDULE OF EVENTS

Assessment/Procedure	Screening Period			Double-Blind Treatment Period ^a			Follow-Up Period	
	SV1	SV2 (3 weeks [±3 days] after SV1)	Baseline Visit (4-7 days after SV2)	Day 1 (not a visit)	M1, 3, 6, 9, 12, 15, 18, 21	Month 24/ EOT Visit	Post-EOT Visit for Subjects off IP ^b	Month 25/ EOS Visit ^c
Obtain informed consent	X							
Review eligibility criteria	X	X	X					
Record demographics	X							
Record prior ULTs, including XOI and dose	X							
Assess AEs	X	X	X		X ^d	X	X	X
Randomize in IVRS/IWRS			X ^e					
Complete medical history			X					
Record concomitant medications			X		X	X	X	X
Administer patient-reported outcomes			X		X (except at M1)	X	X	X
Vital signs	X	X	X		X	X	X	X
Physical examination			X					
Height and weight (BMI)	X					Weight only		
12-lead ECG			X					
Assess gout flares ^f			X		X	X	X	X
Measure target tophi			X		M6, 12, 18	X	X	X
Laboratory Assessments								

Assessment/Procedure	Screening Period			Double-Blind Treatment Period ^a			Follow-Up Period	
	SV1	SV2 (3 weeks [±3 days] after SV1)	Baseline Visit (4-7 days after SV2)	Day 1 (not a visit)	M1, 3, 6, 9, 12, 15, 18, 21	Month 24/ EOT Visit	Post-EOT Visit for Subjects off IP ^b	Month 25/ EOS Visit ^c
Hematology blood collection			X		M6, 12, 18	X	X	X
Serum collection for the following chemistry analyses:								
Analytes 1	X ^g	X ^g	X		X ^d	X	X	X
Analytes 2			X		X	X	X	X
Analytes 3			X		M6, 12, 18	X	X	X
Pregnancy tests ^h		X			M12	X		
Urine collection for the following analyses:								
Urinalysis		X ⁱ	X		X	X	X	X
Protein-creatinine ratio			X		M6, 12, 18	X	X	X
Plasma and urine samples for biomarker collection			X		M6, 12, 18	X		X
Study Medication^j								
Dispense Study Medication (lesinurad/placebo, XOI, colchicine) ^k			X		X (except at M1)	X (XOI only)	X (XOI only)	
Assess compliance with XOI ^l		X	X		X	X	X	X
Assess compliance with gout flare prophylaxis ^m					M3 and 6			
Assess compliance with IP					X	X		
Vital status								X

Abbreviations: AE, adverse event; BMI, body mass index; ECG, electrocardiogram; EOS, End of Study; EOT, End of Treatment; IP, investigational product; IVRS, Interactive Voice Response System; IWRS, Interactive Web Response System; M, study month, SV, Screening Visit; ULT, urate-lowering therapy; XO, xanthine oxidase inhibitor.

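### Does the main eCrCl analysis need a stated on-treatment window so that an early stopper's End of Treatment creatinine is not discarded?

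*Combined protocol and SAP*

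**What the plan says.** Section 9.4.2 names the absolute and percent changes in eCrCl from Baseline to Month 24 as the main estimands for the safety objective. Section 9.4.2.1 adds that, before the MMRM, "renal function data that are collected after subjects discontinue IP will be set to missing". The gaps are filled by multiple imputation under MAR, with a separate model for each arm. The synopsis repeats this.

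Section 8.3.3 times the EOT visit "as soon as possible after permanently discontinuing IP (for subjects who discontinue IP early". Section 8.4 likewise calls for it "as soon as possible after discontinuing IP, then a Post-End of Treatment Visit". Neither sets an outer limit in days. The Appendix A schedule puts EOT in one column with Month 24 under the Double-Blind Treatment Period, and the first column labelled as off drug is "Post-EOT Visit for Subjects off IP".

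On interruptions, section 5.3.2.1 says "An episode is defined as the interruption and then re-initiation of IP, regardless of the duration of the interruption", and section 6.12.2 says "The re-initiation of IP may occur regardless of the duration of the interruption".

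Section 9.4.2.1 also commits to a sensitivity analysis on all available data, including data after discontinuation. It plans a further missing-not-at-random analysis and gives early stopping for worsening renal function as an example. Section 9 opens with "Further details will be provided in the Statistical Analysis Plan (SAP"; the SAP text is not in the combined document.

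**The concern.** If data after discontinuation are deleted and EOT comes after discontinuation, the EOT creatinine is deleted. For a subject who stops between visits because kidney function has worsened, EOT may be the first central laboratory record of that decline. The imputation would then replace it with draws modelled on same-arm subjects who stayed on drug. If such stops are more common on lesinurad, the main safety estimate moves toward no difference.

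Two features sharpen the worry. Appendix A can be read as treating EOT as on-treatment, so two programmers might classify the value differently. The rule also names discontinuation and not interruption, so a value drawn weeks into an interruption stays in while one drawn days after a final dose goes out. Section 3.2.1 lists the last value on and off treatment as an endpoint without defining either term.

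**Working it through.** **Inputs.** Section 9.2: SD 10 mL/min (absolute) and 20% (percent), 95% two-sided. Section 4.1: 300 per arm. Sections 8 and 8.3.2: a month is 28 days, with nine visits at Days 28, 84, 168, ..., 672. The documents give no rate of renal stopping, so the excess share q of lesinurad subjects whose decline is first measured at EOT, and the size D of the drop, are assumptions.

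**1. The plan's precision reproduces.**
- SE = 10 × √(2/300) = 0.816; half-width = 1.96 × 0.816 = 1.60 mL/min.
- Percent scale: 1.96 × 20 × √(2/300) = 3.20%.

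**2. Effect under the literal reading, if the decline would have persisted on drug.** Bias b ≈ q × D. Coverage = Φ(1.96 − b/SE) − Φ(−1.96 − b/SE).

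| q (assumed) | D (mL/min) | b (mL/min) | b / 1.6 | Coverage |
|---|---|---|---|---|
| 1% | 10 | 0.1 | 6% | 94.8% |
| 1% | 20 | 0.2 | 13% | 94.3% |
| 5% | 10 | 0.5 | 31% | 90.6% |
| 5% | 20 | 1.0 | 63% | 76.8% |

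On the percent scale, at an assumed baseline of 45 mL/min, the 1% rows are 0.01 × 10/45 = 0.2 and 0.01 × 20/45 = 0.4 points, against ±3.2.

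**3. Which row is plausible?** A 5% excess means 0.05 × 300 = 15 extra lesinurad subjects with a 10 to 20 mL/min drop never measured on drug. The nearest figure in the documents is indirect: section 1.2.1 reports renal-related serious events in at most 1% of subjects in 12-month studies of a broader population. The mandatory kidney-function criteria in sections 5.3.2.1.1 and 6.12 run on central laboratory results, and mandatory permanent discontinuation for interruptions needs more than three episodes. Subjects on that route normally have earlier measured values, which stay in the model. Under section 6.12 retesting, "as well as the interruption of IP due to safety concerns, can occur any time on study", at the investigator's discretion.

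**4. Would keeping EOT repair it?** Suppose EOT is entered at the next visit that holds no on-drug value (visit k). Its weight on the Month 24 value is its coefficient in the regression of Month 24 on visits 1 to k. With equal correlation r this is r/(1 + r(k − 1)), and 1 at k = 9. Averaging over uniform stop times for r = 0.5:

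(28 × 0.500 + 56 × 0.333 + 84 × (0.250 + 0.200 + 0.167 + 0.143 + 0.125 + 0.111 + 1)) / 672 = 0.298.

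The same sum gives 0.327 for r = 0.7. With correlation decaying at 0.8 or 0.9 per 84 days, the means are 0.519 and 0.711. So about one third to two thirds of a persistent drop comes back.

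That recovery has a price. With EOT drawn 0 to 7 days after stopping, the value moves 36 days on average; 86% move more than 7 days and 42% more than 42 days. Stops after Month 21 (84/672 = 0.125 of stop times, weight 1) supply 0.125/0.298 = 42% of the recovery at r = 0.5 and 0.125/0.327 = 38% at r = 0.7, simply by relabelling EOT as Month 24. Under plain nearest-visit mapping, 43.8% of EOT values land on a visit already filled; if the earlier value wins, the mean weights fall to 0.171 to 0.394.

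**5. If the decline would have resolved on drug.** The target contribution is then 0. The literal rule is about unbiased, and keeping EOT adds error of weight × q × D: from 0.298 × 0.1 = 0.03 to 0.711 × 0.2 = 0.14 mL/min at 1%, and 0.15 to 0.71 at 5%. Section 1.2.1 describes this pattern: creatinine rises that generally resolved, most without interruption.

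**The case for a change.** The best case for a change is that this is the main safety analysis, the inclusion rule can be read in two ways, and a few words would settle it. Section 9.4.2.3 considers an attribution window for MACE, but nothing similar appears for eCrCl. The ±7 days is a scheduling tolerance and the 28 days is for adverse event collection. Fixing the rule before unblinding removes any room for a results-driven choice, and the EOT sample is already scheduled.

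Much of this is true. The protocol gives no window after the last dose, and for an interrupted subject who never restarts it does not say whether discontinuation dates from the last dose or from the later decision. Two parts do not carry through. Appendix A is a schedule of procedures, not an analysis rule, so it does not contradict section 9.4.2.1; a deletion rule without a window is a zero-day rule, and section 5.3.2.1.2 requires the discontinuation date to be recorded. The treatment of values drawn during interruptions is a choice about intercurrent events, and keeping them is not an error. What remains is detail that a SAP normally supplies.

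**Conclusion.** This is a gap that analysts fill in the SAP in the usual way, and following section 9.4.2.1 as written would still leave the conclusion sound. At the only excess the documents indirectly suggest, about 1%, the main estimate moves 0.1 to 0.2 mL/min and coverage is 94.3% to 94.8%. That excess is itself an assumption, drawn from serious renal events in a broader population. Larger effects need roughly a 5% excess, for which the documents offer no support.

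Even the direction is conditional: a lean toward no harm needs both more such stops on lesinurad and declines that would have persisted on drug. If they would have resolved, keeping the EOT value makes the estimate worse. Neither classification is clearly better.

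The information is not lost. The all-data sensitivity analysis retains EOT, the missing-not-at-random analysis has this group in view, and the endpoints on creatinine elevation, discontinuation criteria and renal events (sections 3.2.1 and 9.4.2.2) would show an excess of renal harm. No change to the plan follows.

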3.2. Study Endpoints

3.2.1. Safety Endpoints

- Absolute and percent change from Baseline in eCrCl to Month 24.
- Absolute and percent change from Baseline in eCrCl over the study period, including the last value on and off treatment.
- Incidence of sCr elevations ($\geq 1.5 \times$ Baseline) over the study period.
- Incidence of subjects meeting criteria (eg, based on sCr or eCrCl criteria) for treatment discontinuations over the study period.
- Incidence of renal-related and kidney stone TEAEs and SAEs.
- Prevalence of contributing factors to renal SAEs as adjudicated by the REAC.
- Incidence of CEAC-adjudicated MACE (CV death, nonfatal myocardial infarction, and nonfatal stroke).
- Incidence of CEAC-adjudicated MACE or hospitalization for unstable angina (MACE+).

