5.3.2.1.2. Other Reasons, and Procedures, for Permanent Discontinuation of Investigational Product

As much as possible and permitted by the protocol, subjects should be encouraged to continue on IP for the full 24-month Treatment Period.

Subjects have the right to permanently discontinue IP at any time for any reason. Investigators may also discontinue IP if they determine that it is not in the best interest of the subject to continue. All subjects should be encouraged to remain in the study even if IP has been discontinued for any reason.

IP must be permanently discontinued if the subject meets any of the following criteria:

- Subject permanently discontinues XOI.
- Subject becomes pregnant.
- Subject initiates chronic therapy with any of the following medications:
 - valpromide, progabide, valproic acid, or other known inhibitors of epoxide hydrolase.
 - any approved ULT indicated for the treatment of gout (eg, benzbromarone, probenecid, pegloticase, commercially-available lesinurad), except those required per protocol (allopurinol and febuxostat).
 - azathioprine or mercaptopurine.
- Subject requires dialysis or kidney transplantation.
- Subject has temporarily interrupted IP for more than 3 separate episodes at any time on study due to changes in kidney function, based on any safety concern due to IP by the Investigator or Healthcare Provider, or where protocol-specified criteria for interruption have been met (ie, sCr \geq 4.0 mg/dL or an eCrCl $<$ 20 mL/min).

The date and the reason must be recorded on the appropriate Case Report Form (CRF) for all subjects who discontinue IP. If the reason is an AE, the specific AE must be identified on the CRF.

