Subjects who permanently discontinue IP early should complete an End of Treatment Visit (Section 8.3.3) as soon as possible followed by a Post-End of Treatment Visit (Section 8.4.1) 1 month after the End of Treatment Visit. Subjects should then continue on study and follow the protocol-defined schedule of events, through Month 24. The subject has the option to continue on study-supplied XOI during this time. Although all assessments are encouraged, at a minimum, it is requested that collection of AEs and collection of a blood sample for Analytes 1 (see Table 1) occur. Alternatively, if the subject does not agree to this option, a modified follow-up including, eg, regular telephone contacts or a contact at Month 24, should be arranged, if agreed to by the subject and in compliance with local data privacy laws/practices. Subjects who do not wish to continue on study after discontinuing IP should complete an End of Study Visit (Section 8.4.2) 1 month after treatment discontinuation.

If IP is permanently discontinued prior to the Month 6 study visit, then gout flare prophylaxis should also be discontinued.

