6.9.1. Clinical Safety Laboratory Assessments

Blood and urine samples will be collected for clinical safety laboratory tests (hematology, serum chemistry, and urinalysis) and will be tested by a central laboratory. Any clinical safety laboratories results post-Baseline that are considered possibly significant may be repeated (see [Section 6.12](#)).

See [Table 1](#) for a list of clinical safety laboratory tests.

Table 1: Clinical Safety Laboratory Tests

Hematology:
 
 • Hematocrit • Hemoglobin • Mean corpuscular hemoglobin • Mean corpuscular hemoglobin concentration • Mean corpuscular volume • Platelet count • Red blood cell count • Red blood cell morphology • White blood cell count with differential 
Urinalysis:
 
 • Appearance • Bilirubin • Color • Glucose • Ketones • Nitrite • Occult blood • pH • Protein • Specific gravity • Urobilinogen • Microscopic examination of sediment including uric acid crystals 
Additional urine analyses:
 
 • Creatinine • Total protein 	
Serum Chemistry:
 
Analytes 1
 
 • Blood urea nitrogen • Creatinine (enzymatic method) • Glucose • Uric acid^a 
Analytes 2
 
 • Albumin • Calcium • Carbon dioxide • Chloride • Phosphorus • Potassium • Sodium • Total cholesterol • Triglycerides 
Analytes 3
 
 • Alkaline phosphatase • Alanine aminotransferase • Aspartate aminotransferase • Total bilirubin • Creatine kinase 
Pregnancy and fertility testing
 
 • Human chorionic gonadotropin^b • Follicle-stimulating hormone^c
---	---

^a Serum uric acid (sUA) will be used for efficacy analyses. All study personnel, except for those defined in Section 5.5, will be blinded to sUA results collected after Baseline through database lock.

^b At Screening Visit 2 for all females and again at Month 12 for all females except those who are surgically sterile or not of childbearing potential as confirmed by the Screening Visit 2 follicle-stimulating hormone test.

^c At Screening Visit 2. Only for females with 12 months of spontaneous amenorrhea who are not surgically sterile.

Estimated CrCl at each visit will be calculated by the Cockcroft-Gault formula using ideal body weight (based on height measured at Screening) as follows:

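### The all-data sensitivity analysis and the last off-treatment eCrCl would take creatinine drawn after maintenance dialysis or a kidney transplant at face value, which errs toward less renal harm

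*Combined protocol and SAP*

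**What the plan says.** The relevant statements are spread over several protocol sections.

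- **Stopping IP (5.3.2.1.2).** One mandatory reason for permanent discontinuation is "Subject requires dialysis or kidney transplantation". This stops treatment and is not a study exit: "All subjects should be encouraged to remain in the study even if IP has been discontinued for any reason". Section 6.16 lists only consent withdrawal, death and loss to follow-up as possible reasons for leaving the study.
- **Data after IP (5.3.2.1.2, repeated in 8.3.2).** All assessments are encouraged, but "at a minimum, it is requested that collection of AEs and collection of a blood sample for Analytes 1" should occur. Table 1 in Section 6.9.1 lists creatinine under Analytes 1.
- **Derivation (6.9.1).** "Estimated CrCl at each visit will be calculated by the Cockcroft-Gault formula using ideal body weight". No exception is made for dialysis or transplant.
- **Main analysis (9.4.2.1).** Before the MMRM, "renal function data that are collected after subjects discontinue IP will be set to missing", and missing values are multiply imputed under MAR separately by arm.
- **Sensitivity analyses (9.4.2.1).** The first reads: "Sensitivity analysis will include all available data (including data after subjects discontinue IP) and impute only for missing data assuming MAR". A second, under missing not at random (MNAR), is to depend on the pattern of missing data and early discontinuation. It gives worsening renal function as an example, but its rule is not fixed.
- **Endpoint (3.2.1).** "Absolute and percent change from Baseline in eCrCl over the study period, including the last value on and off treatment".

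Section 9.4.2.2 lists the proportion of subjects requiring dialysis only as an assessment that may be included, and does not name transplant. Section 4.3 excludes transplant recipients at entry only.

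**The concern.** Once a subject is on maintenance dialysis or has a working graft, serum creatinine reflects clearance by the machine or the donor kidney. Cockcroft-Gault applied to it no longer estimates the function of the subject's own kidneys. In both cases creatinine is lower than it would otherwise be, so the calculated eCrCl is too high.

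The all-data analysis is the one specified eCrCl model that uses what was actually observed after IP stopped. The last off-treatment value has a similar purpose at subject level. Following the stated rules exactly would put invalid values into both, in the subjects with the worst renal outcome, in a trial whose primary objective is safety with a focus on the kidney. The same applies to any eGFR version run by similar methods under Section 9.4.2.1.

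**Working it through.** **1. The plan's own precision.** Section 9.2 gives a half-width of 1.6 mL/min for the arm difference in absolute change, with SD 10 and 300 per arm. Check: 1.96 x 10 x sqrt(2/300) = 1.60. For percent change with SD 20: 1.96 x 20 x sqrt(2/300) = 3.20. Both reproduce.

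**2. One transplant subject.** The patient values are assumed; the documents give none. Take a man with ideal body weight 70 kg and use the male formula in Section 6.9.1, (140 - age) x weight / (72 x sCr).

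| Time | Age | sCr (mg/dL) | eCrCl (mL/min) |
|---|---|---|---|
| Baseline | 68 | 2.0 | 72 x 70 / 144 = 35.0 |
| Kidney failure | 69 | 6.0 | 71 x 70 / 432 = 11.5 |
| After transplant | 70 | 1.4 | 70 x 70 / 100.8 = 48.6 |

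The change used would be 48.6 - 35.0 = +13.6 (about +39%). The change at kidney failure was 11.5 - 35.0 = -23.5 (about -67%). The error is 48.6 - 11.5 = 37.1 mL/min.

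**3. One dialysis subject.** Assume a man of 65 with ideal body weight 70 kg, Baseline eCrCl 40, and creatinine on dialysis of 4, 6 or 8 mg/dL. Then 75 x 70 / (72 x sCr) gives:

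- sCr 4: 18.2 mL/min, change -21.8 (-54%)
- sCr 6: 12.2 mL/min, change -27.8 (-70%)
- sCr 8: 9.1 mL/min, change -30.9 (-77%)

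The decline is understated, but each value is still a fall of more than half from Baseline.

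**4. Effect on the arm difference.** Suppose one arm has k more affected subjects than the other, and each used value is too high by S mL/min. The difference then moves by k x S / 300.

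| Event | Assumed S | Shift per excess subject | Excess needed to move 1.6 (480 / S, rounded up) |
|---|---|---|---|
| Dialysis | 5 | 0.017 | 96 |
| Dialysis | 10 | 0.033 | 48 |
| Transplant | 30 | 0.10 | 16 |
| Transplant, step 2 | 37.1 | 0.12 | 13 |
| Transplant | 50 | 0.17 | 10 |

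The documents give no rate for dialysis or transplant. The nearest figure is in Section 1.2.1: renal-related serious TEAEs in at most 1% of subjects in the 12-month Phase 3 studies. That would be about 3 in an arm of 300, but it covers a broader event class, a broader population and a shorter period.

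**5. Direction.** For each affected subject the error is toward less harm. For the arm difference, its sign depends on which arm has the excess. It hides harm from lesinurad only if the excess is in the lesinurad arm.

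**The case against.** The case against giving this much weight has several parts, and most of them stand.

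- **Recovery.** A reader might infer that dialysis and transplant are both scored as recovery. On the assumed values, only the transplant is. Dialysis values still show a large fall.
- **Mean difference.** A reader might apply the transplant error to three to five excess cases and get 3 x 37.1 / 300 = 0.37 to 5 x 37.1 / 300 = 0.62 mL/min. That requires every excess case to reach kidney failure and have a well-functioning graft before Month 24. With the dialysis errors above, three to five cases move the difference by 3 x 5 / 300 = 0.05 to 5 x 10 / 300 = 0.17. No event rate in the documents supports either count.
- **Main result.** A reader might infer that the main eCrCl analysis is contaminated. It is not, because values after IP stops are removed before the MMRM.
- **MNAR analysis.** This is planned and could address these subjects within the main dataset, where their post-IP values count as missing. It would not by itself correct the all-data set, where the values are observed, and its rule is still open.
- **Visibility.** The event is not lost. It can count as a creatinine elevation of at least 1.5 x Baseline (step 2 has a threefold rise) and as a renal AE or SAE, with blinded adjudication of serious cases (9.4.2.2, 11.8.2). That does not correct the eCrCl results.
- **Availability.** Staying on study is encouraged and bloods are requested. Modified follow-up, such as telephone contact, is allowed, so some subjects will have no such creatinine.
- **Level of detail.** Section 9 defers details to the SAP. No separate SAP text is in the supplied document, so a rule there cannot be ruled out. Still, the stated rule to use all available data covers these values as it stands.

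**Conclusion.** The point holds in a limited form. As written, the all-data sensitivity analysis and the last off-treatment eCrCl would use creatinine taken after maintenance dialysis or transplant as if it measured native kidney function, with a known direction of error for each subject. A transplant can look like recovery; dialysis makes a severe decline look less severe.

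The documents do not support a claim that the main eCrCl estimate is biased by these values, that kidney failure disappears from the safety reporting, or that the mean difference would move materially. On assumed inputs the shift is about 0.02 to 0.03 mL/min per excess dialysis case and about 0.12 per excess transplant case, against a half-width of 1.6. The damage is mainly to subject-level and last-value summaries, where one subject can be wrong by about 37 mL/min in the transplant example.

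Confidence in the gap is high, subject to the SAP to which the protocol defers. Confidence in the size is low, because event counts and post-event creatinine values are all assumed. The gap should be closed before unblinding.

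**What to change.** State in Section 9.4.2.1 and in the SAP, before unblinding:

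1. eCrCl and eGFR from the first maintenance dialysis or kidney transplant onward are not used as observed. The SAP defines maintenance dialysis for analysis purposes, since the protocol does not. Limiting the rule this way keeps genuine recovery after temporary dialysis.
2. In the all-data sensitivity analysis and the last off-treatment value, those visits receive a prespecified unfavourable value, for example the last pre-event value, with a fixed low kidney-failure value as the alternative. Both should be run, because the last pre-event value is unfavourable only if it was taken close to the event.
3. The number of subjects with maintenance dialysis or transplant is reported by arm as a required output, not an optional one.

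The cost is small. It is mainly wording, plus a check that CRF or AE records hold dialysis and transplant dates. The IP-discontinuation record is not enough, because a subject who stopped IP earlier for another reason would have no dialysis or transplant date there. The one real drawback is that the assigned value is a convention, so the report should label it as such.
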